3. STUDY OBJECTIVES AND ENDPOINTS

Study objectives and endpoints from the protocol are described below, with added detail.

3.1. Study Objectives

3.1.1. Primary Objective

The co-primary objectives of the study are to demonstrate the non-inferiority of Cecolin[®] administered on 0, 6-month; 0, 12-month; and 0, 24-month two-dose regimens, to Gardasil[®] using a 0, 6-month two-dose regimen, based on HPV Immunoglobulin G (IgG) antibody levels measured one month after the last dose for HPV types 16 and 18. Bonferroni correction will be used to adjust the type I error rate for the multiple comparisons. The analyses will use anti-HPV 16 and 18 IgG antibody GMCs, measured by ELISA.

3.1.2. Secondary Objectives

The secondary (exploratory) objectives are to:

- Evaluate immunogenicity of Cecolin® and Gardasil®, in all study arms, based on a functional assay pseudovirion-based neutralization assay (PBNA) to measure antibody levels at all time points.
- Describe seroconversion rates one month after the last dose of Cecolin[®] (all schedules: (0, 6-month; 0, 12-month; and 0, 24-month)) and after the last dose of Gardasil[®] (0, 6-month schedule).
- Evaluate the non-inferiority of a mixed 2-dose regimen consisting of a single dose of Gardasil[®] followed by a single dose of Cecolin[®] given 24 months later (0, 24-month schedule), to Gardasil[®] using a 0, 6-month two dose regimen for HPV types 16 and 18
- Evaluate the non-inferiority of Cecolin[®] administered on 0-6 months to Gardasil[®] given on a 0-6-month schedule at 24 months post-first dose
- Evaluate the safety of Cecolin[®] in 9-14-year-old females across multiple geographies administered in two-dose regimens.

3.1.3. Exploratory Objectives

The exploratory objectives are as follows:

- Conduct anti-HPV antibody kinetic modeling based on measurements at baseline, at the time of second dose, and one month after the second dose to determine dose response curves and optimized windows for length of the dose interval
- Conduct immunologic bridging to external data (as they become available) from ongoing reduced-dose efficacy studies by ELISA or PBNA at the time of the second dose and one month after the second dose
- Evaluate the persistence of antibody responses following a single dose of either Gardasil[®] or Cecolin[®] at 6, 12, and 24 months

3.2. Study Endpoints

3.2.1. Primary Endpoints

Anti-HPV 16 and 18 IgG antibody geometric mean concentration (GMC), measured by enzyme-linked immunosorbent assay (ELISA) one month after the second dose on Month 7 (for the 0, 6-month arms), Month 13 (for the 0, 12-month arm) or Month 25 (for the 0, 24- month arm) following vaccination. The GMC ratios (Cecolin arm/Gardasil 0, 6) and corresponding two-sided 98.3% CI for each comparison will be computed.

3.2.2. Secondary Endpoints

3.2.2.1. Secondary Immunogenicity Endpoints

- Anti-HPV 16 and 18 serum neutralizing antibody geometric mean titer measured by PBNA compared to ELISA at all time points (in a representative subset).
- Seroconversion rate, defined as a 4-fold rise in anti-HPV 16 and 18 IgG antibody as measured by ELISA, at baseline and one month following the last dose.
- Anti-HPV16 and 18 IgG antibody GMC measured by ELISA one month following the last dose of the Gardasil[®] 0-6-month two dose regimen and the Gardasil[®]-Cecolin[®] 0-24-month two dose regimen.
- Anti-HPV16 and 18 IgG antibody GMC measured by ELISA 24 months following the first dose of the Gardasil® 0-6-month two dose regimen and the Cecolin® 0-6-month two dose regimen.

The corresponding two-sided 95% CI for each metric will be computed.

3.2.2.2. Secondary Safety Endpoints

- Number of subjects in each study arm reporting solicited adverse events within 7 days after each dose
- Number of subjects in each study arm reporting unsolicited adverse events within one month after each dose
- Number of subjects in each study arm reporting serious adverse events (SAEs) occurring at any time throughout study participation

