	immunosuppressive corticosteroids are any parenteral corticosteroid, high dose (>800 mcg/day) beclomethasone dipropionate or equivalent medication. Nasal and topical steroids are allowed.
	9. Allergies to any components of the vaccines 10. Current or former participation in HPV vaccine related research. 11. Prior receipt of an investigational or licensed HPV vaccine
	12. Any other condition(s) that in the opinion of the investigator would jeopardize the safety or rights of a participant participating in the trial or would render the participant unable to comply with the protocol
Study population	1025 girls (205 per arm) 9-14 years of age

Number of participating sites	Two sites recruited from icddr,b in Bangladesh in South/Southeast Asia and MRC in Ghana in Africa		
Study Duration	Overall study duration will be approximately 30 months, assuming a 5- to 6-month period of enrollment.		
Participant Duration	Study participation for each individual will be dependent on treatment assignment; either 13, 24, or 25 months.		
Safety Monitoring	Throughout the study, the site investigators will provide continuous monitoring to identify, evaluate, and manage adverse events.		
	PATH Medical Officer and CRO medical monitors on an on-going basis will review all severe AE's and Serious Adverse Events (SAE's). The CRO Data Monitoring Center (DMC) will provide periodic safety reports of accruing safety data for review. All SAEs will be reported to local ethics committees, WCG IRB and regulatory authorities, as required.		
	A PATH Data and Safety Monitoring Board (DSMB) formed by independent vaccine, pediatric and infectious disease experts, as well as a biostatistician, will be established to periodically review cumulative data. The responsibilities and procedures of the DSMB will be defined in a DSMB Charter. The PATH DSMB will be responsible for safeguarding the interests of trial participants, assessing safety during the trial, and for monitoring the overall conduct of the clinical trial.		
Statistical	Sample Size		

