# 6.2.8 Visit 7: Day 730±28 Visit: (Groups 1 and 4)

18 months after the second vaccination for Groups 1 and 4:

- Confirm ongoing consent/assent and continued eligibility prior to performing any study procedures.
- Any topics or new information considered by site PI to be important to continued informed consent will be shared with the participant.
- Review to confirm that any ongoing unsolicited AEs at the time of the last visit have resolved and for any SAEs that have occurred since the last visit
- Update the medical history and concomitant medications as necessary
- Record oral or axillary temperature, pulse, respiratory rate and blood pressure
- Conduct a full physical examination
- Collect 10 mL of whole blood for immunological testing
- Exit participants in Groups 1 and 4 from the study.

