# 6.2.9 Visit 4: Day 365±28 Visit: (Group 2)

One year after the first vaccination for Group 2:

- Confirm ongoing consent/ assent and continued eligibility prior to performing any study procedures.
- Any topics or new information considered by site PI to be important to continued informed consent will be shared with the participant.
- Review to confirm that any ongoing unsolicited AEs at the time of the last visit have resolved and for any SAEs that have occurred since the last visit
- Update the medical history and concomitant medications as necessary
- Record oral or axillary temperature, pulse, respiratory rate and blood pressure
- Conduct a full physical examination
  - Perform urine pregnancy test for women of childbearing potential
- Collect 10 mL of whole blood for immunological testing prior to vaccination
- Verify study treatment assignment and administer study vaccination according to the procedures outlined in the study Day 1 visit.
- Observe subject for 30 minutes for immediate reactogenicity, post vaccination check for solicited adverse event / reactogenicity per section 8.1.1
- Before discharge from the study clinic, the participant will be provided with a memory aid to record solicited AE information for the next 7 days, and follow-up visit information and contact telephone numbers for study staff will be provided. Participants are to be instructed to contact study staff for any solicited AE greater than mild.
- Participants will be called or visited in their homes daily through 7 days post-vaccination to verify daily completion of the memory aid.

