# 6.2.11 Visit 6: Day 395+7 Visit: (Group 2)

One month after the second vaccination for Group 2:

- Confirm ongoing consent/assent and continued eligibility prior to performing any study procedures.
- Any topics or new information considered by site PI to be important to continued informed consent will be shared with the participant.
- Study clinician will review and record the participant's interval health history, medication use
  and the participant's assessment of the post-vaccination experience, including a review of
  ongoing solicited AEs and unsolicited AEs one month following dose 2, through personal
  interview and assisted by the memory aid.
- Findings of study clinician suggesting inaccuracy of reported self-assessments will be clearly documented.
- Provide care to participants or refer them for further treatment with any ongoing AEs or SAEs, as required.
- Collect memory aid for filing in the participant file.
- Record oral or axillary temperature, pulse, respiratory rate and blood pressure
- Targeted physical examination, if indicated based on review of medical history
- Collect 10 mL of whole blood for immunological testing
- Exit participants in Group 2 from the study.

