# 8.2 Reporting Period and Parameter

Safety events are reported from the time of the first study injection through completion of the study. Specifically, solicited AEs to assess local and systemic reactogenicities will be collected at 30 minutes and then daily for 7 days after each vaccination. If a solicited AE started during the 7 days post vaccination and continues beyond the 7 days, it will continue to be reported as a solicited AE until resolution. Unsolicited AEs will be collected from Day 1 to the 30-day post vaccination visit after each vaccination. SAEs will be assessed from Day 1 through the end of the study for

each group. Any medical condition that is present at the time that the participant is screened will be considered as baseline and not reported as an AE. AEs characterized as intermittent require documentation of onset and duration of each episode.

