4.5.2.4. Serious Adverse Event (SAE) or Suspected Unexpected Serious Adverse Reaction (SUSAR)

Serious adverse event is any adverse event that results in any of the following outcomes:

- 1. Death
- 2. Is life-threatening (life-threatening means that the study participant was, in the opinion of the site PI or Sponsor, at risk of death at the time of the event; it does not refer to an event which hypothetically might have caused death if it were more severe).
- 3. Requires inpatient hospitalization or prolongation of existing hospitalization
- 4. Results in persistent or significant incapacity or substantial disruption of the ability to conduct normal life functions
- 5. Congenital abnormality or birth defect
- 6. Important medical event that may not result in one of the above outcomes but may jeopardize the health of the study participant or (and) require medical or surgical intervention to prevent one of the outcomes listed in the above definition of serious adverse event

SAEs are collected from the time of first vaccination through the end of the study for each.

Suspected unexpected serious adverse reaction (SUSAR) is any suspected adverse reaction that is both unexpected and serious.

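### Group 2's all-study SAE percentage covers about 13 months and is not comparable with the 24-25 months behind the other arms; the SAP text should show follow-up and a common cut-off

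*SAP*

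**What the plan says.** The endpoint in SAP 3.2.2.2 is the "Number of subjects in each study arm reporting serious adverse events (SAEs) occurring at any time throughout study participation". It has no time limit. SAP 4.5.2.4 states that "SAEs are collected from the time of first vaccination through the end of the study for each", where the sentence breaks off. Protocol 8.2 supplies the sense: "SAEs will be assessed from Day 1 through the end of the study for" each group.

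The end of study differs by arm. The Protocol Summary says: "Study participation for each individual will be dependent on treatment assignment; either 13, 24, or 25 months". Protocol 6.2.11 ("Visit 6: Day 395+7 Visit: (Group 2") ends with the instruction "Exit participants in Group 2 from the study". Protocol 6.2.8, the Day 730 visit, says "Exit participants in Groups 1 and 4 from the study". Protocol 6.2.14 does the same for Groups 3 and 5 at Day 760.

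SAP 9.1.2 gives tables as subjects, percentage and events, with each group's total vaccinated population as denominator. SAP 9 adds Clopper-Pearson intervals. SAP 12 announces extra versions of two tables, covering all SAEs and unsolicited AEs and not just those within 30 days of a dose. They are numbered 89 and 97 and go to the public registry. SAP 9.1.2 places Table 89 in the overall AE summary range (86-89), Table 97 in the by-severity range (90-97), and SAE summaries by organ class in Tables 108-110.

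**The concern.** Percentages with the same kind of denominator will stand side by side by arm, yet one arm is observed for little more than half as long as the control. With no true difference, a Cecolin arm would be expected to show a lower SAE percentage than Gardasil simply because it is watched for less time. A confidence interval for each percentage reflects sampling error and gives no sign of this. At stake is the correct reading of a named safety endpoint, above all in the registry tables, where a reader may not have the visit schedule at hand.

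**Working it through.** **The plan's own figure.** Protocol 11.3 and SAP 5 state a probability above 90% of seeing at least one severe or serious AE in an arm of 205 at a risk of 1.2%. 1 - (1 - 0.012)^205 = 91.6%, so it reproduces. The statement gives no follow-up length. If 1.2% is read as a 24-month risk, a constant hazard gives 0.651% by Day 395, and the probability in Group 2 is 73.8%.

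**Planned follow-up.** Person-years = 205 x days / 365.25, without dropout:
- Group 2: 395 days, 221.7
- Groups 1 and 4: 730 days, 409.7 each
- Groups 3 and 5: 760 days, 426.6 each

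Ratios: 395/730 = 0.541 and 395/760 = 0.520. With the planned 15% dropout accruing at a constant rate to Day 760 (an assumption), Group 2 has 212.6 person-years against 379.3 in Group 4, a ratio of 0.560.

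**Expected percentages, equal constant hazard.** Risk = 1 - exp(-rate x days / 365.25). The documents give no SAE rate specific to ages 9-14. Their nearest figure is in Protocol 1.5.2: 3 of 979 girls and women aged 9-26 over 7 months. 3 / (979 x 7/12) = 0.525 per 100 person-years (exact 95% CI 0.108-1.535). A range of rates is therefore assumed:

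| Rate per 100 person-years | Group 2 | Group 4 | Ratio | Expected girls with an SAE, Group 2 v Group 4 |
|---|---|---|---|---|
| 0.25 | 0.270% | 0.498% | 0.542 | 0.6 v 1.0 |
| 0.5 | 0.539% | 0.994% | 0.542 | 1.1 v 2.0 |
| 1.0 | 1.076% | 1.979% | 0.544 | 2.2 v 4.1 |
| 1.5 | 1.609% | 2.953% | 0.545 | 3.3 v 6.1 |

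Against Groups 3/5 the ratio is 0.520-0.524.

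**If SAEs cluster after doses.** Let the hazard be m times higher in the 30 days after each of two doses (m is an assumption). Group 2 then has weight 60m + 335 and Group 4 has 60m + 670.
- Crude ratio: 455/790 = 0.58 (m = 2), 635/970 = 0.65 (m = 5), 935/1270 = 0.74 (m = 10).
- Person-year rate ratio (crude ratio x 730/395): 1.06, 1.21, 1.36. With no true difference, a rate alone would make Group 2 look worse.
- Day 1-395 percentage on scheduled days: Groups 1, 2 and 4 all have weight 60m + 335, so the ratio is 1.00 at any m. Groups 3 and 5 have had one dose, with weight 30m + 365, which is 0.81 (m = 5) or 0.71 (m = 10) of Group 2's.

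**Sensitivity to visit timing.** Protocol 6.2.9 allows dose 2 in Group 2 from Day 337 to Day 393 (365 ± 28). Suppose the last visit follows the actual dose by 30-37 days, which is an inference and not a printed rule. With dose days spread evenly, the Day 1-395 ratio of Group 2 to Group 4 becomes 0.99 (m = 1), 0.95 (m = 5) and 0.93 (m = 10).

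**Precision.** Clopper-Pearson 95% intervals are 0.01-2.69% for 1/205 and 0.12-3.48% for 2/205. They overlap almost entirely.

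**The case against.** The strongest case against has four parts.

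- *The endpoint is a per-arm count, and n (%) is correct for it.* This stands. A reader might infer that Group 2's percentage is a biased estimate. It is not: it is right for what it counts, and the documents define no between-arm SAE contrast for it to bias. The fault is lack of comparability once arms are set side by side.
- *The vaccine-safety question is largely covered already.* This mostly stands. SAP 12 implies that the base tables are limited to 30 days after each dose, a window equal in all arms, and Listing 15 gives the day post-dose of each SAE. The distortion comes only from later SAEs. But the named endpoint and the SAP 12 versions go beyond those windows, and a listing of events supplies no follow-up denominator.
- *Counts are small and a rate has its own distortion.* Also true. At about 0.5 per 100 person-years the expected difference is roughly one girl. Exact Poisson intervals would be as wide as the crude ones: about 0.01-2.5 per 100 person-years for 1 event in 222, and 0.06-1.8 for 2 in 410. A rate should therefore be a supplement, with the common cut-off as the main comparison.
- *The shells may already show exposure.* The SAP preface makes sample tables part of the plan, and they were not supplied. A reader might infer that no exposure summary exists anywhere; only its absence from the supplied text can be asserted.

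A reader might also infer from the visit windows that Group 2 exits between Day 367 and Day 430. The protocol prints the visit as Day 395 + 7. The wider range requires anchoring it to the actual dose-2 date, which the one-month wording makes plausible but no section states as a window rule.

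**Conclusion.** The point holds as a reporting weakness and should be corrected. The all-study SAE percentage in Group 2 is not like for like with the other arms, because the design gives it 54% of the planned follow-up of Groups 1/4 and 52% of that of Groups 3/5. The expected crude ratio to Group 4 is 0.54-0.55 under an equal constant hazard without dropout, and rises to 0.58-0.74 if the hazard is 2 to 10 times higher after doses. In all these scenarios Group 2 shows the lower percentage.

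The stronger reading, that the plan leads to a wrong safety test or an inflated error rate, is not supported. The only between-group safety test in the supplied text is the Fisher test on solicited events (SAP 9.1.1). The sizes rest on assumed hazards, and the conclusion about what is missing is limited to the supplied SAP text.

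**What to change.** In SAP 9.1.2, for the all-study SAE summary (Table 89, and Tables 108-110 if they cover all follow-up, which the text should state):

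1. Keep n (%) and footnote planned and actual follow-up per arm.
2. Add n (%) with an SAE from Day 1 to Day 395, as the like-for-like comparison of Group 2 with Groups 1 and 4. Note that Groups 3 and 5 have had one dose by then, that actual dose-2 and exit days vary, and that SAEs after Day 395 are left out. Do not write an exit range of Day 367-430 as if it were a protocol rule.
3. As a supplement, add person-years from Day 1 to first SAE or exit, and subjects with an SAE per 100 person-years with an exact Poisson 95% CI. Note that this assumes a roughly constant hazard and would make Group 2 look worse if SAEs cluster after doses.
4. State that items 2 and 3 are read together.

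In Table 97, which lies in the by-severity range, add only the follow-up footnote. Reconcile the reference to Table 84 in SAP 12 with SAP 9.1.1, which gives that number to injection-site features. If the shells already carry exposure, it is enough to say so in 9.1.2 and add the Day 1-395 row.

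The cost is SAP wording, a few rows and footnotes. Vaccination dates and SAE onset dates are already recorded, and exit is a study visit. Conduct, sample size and tests are unchanged. The downside is a longer table in which neither added summary is sufficient alone.

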3.2.3. Exploratory Endpoints

Exploratory endpoints include:

- HPV IgG GMC by ELISA and GMT by PBNA at baseline, at the time of second dose, and one month after the second dose (for immunologic bridging and kinetic modeling)
- HPV IgG GMC by ELISA following a single dose of Gardasil[®] or Cecolin[®] at 6, 12, and 24 months

3.3. Study Definitions and Derived Variables

Definitions and Derivations Used in This Study:

- A baseline value will be defined as the last value obtained prior to the first vaccination of study product.
- Age will be calculated from the date of first vaccination and will be presented in whole years.
- Fever: temperature $\geq 38.0^{\circ}$ C or 100.4° F.
- For immunology, reciprocal endpoint titers less than the lower limit of quantitation (LLOQ) of the assay will be assigned a value of half the starting dilution, and those greater than the upper limit of quantitation (ULOQ) will be assigned a value equal to the ULOQ for computational purposes, except when using analysis methods that incorporate censoring.
- Seroconversion will be defined as a 4-fold rise in anti-HPV 16 and 18 IgG antibody (as measured by ELISA) compared to the baseline titer.
- Seropositive will be defined as a titer value for the ELISA assay of > 8 EU/mL for HPV-16 and >7EU/mL for HPV-18. For the PBNA assay, any IC₅₀ titers that are \geq 21 (HPV-16) or \geq 16 (HPV-18) will be considered as positive titers.

4. INVESTIGATIONAL PLAN

4.1. Overall Study Design and Plan

This randomized, active-comparator controlled, open-label Phase 3 study will enroll approximately 1025 girls aged 9 to 14 years in one country in Africa (Ghana) and one country in South/Southeast Asia (Bangladesh).

Subjects will be randomized 1:1:1:1:1 to one of the following groups to receive Cecolin[®] and/or Gardasil[®]. Each group will consist of 205 subjects.

- Group 1: Cecolin[®] at 0 and 6 months,
- Group 2: Cecolin[®] at 0 and 12 months,
- Group 3: Cecolin[®] at 0 and 24 months,
- Group 4: Gardasil[®] at 0 and 6 months (control), or
- Group 5: Gardasil[®] at 0 months and Cecolin[®] at 24 months.

For each arm, blood will be collected for immunologic testing at baseline and one month following second dose. Additional blood collections will occur immediately prior to the administration of the 6-month, 12-month or 24-month dose for immunobridging to other published and ongoing trials and 24 months after the first dose in groups 1 and 4 for noninferiority comparison.

The clinical protocol time and events schedule is shown in Table 1, Appendix A and a copy of the study schematic is shown below.

Figure A.1 Study Schematic

4.2. Discussion of Study Design

CVIA 087 is a phase 3 randomized, active-comparator controlled, open-label trial to evaluate the immunogenicity and safety of alternate two-dose regimens of a bivalent HPV vaccine (Cecolin[®]) compared to a licensed quadrivalent HPV vaccine (Gardasil[®]) in healthy 9-14 year-old girls in low and low-middle income countries (LMIC). Gardasil[®] is chosen as the comparator vaccine, as this vaccine is the most widely used in LMICs. This study was designed to evaluate non-inferiority data and collect additional safety data. This study design will also permit an exploratory evaluation of a single dose of the vaccine for as long as 24 months, and the performance of a mixed regimen of Gardasil[®] and Cecolin[®] which will be administered 24 months apart.

